#### 14.0 BIOSTATISTICS

#### **Primary objectives:**

The primary objective of this pilot study is to assess the complete response (CR) rate to pembrolizumab in untreated ENKTL following pembrolizumab. Patients who receive any number of cycles of pembrolizumab and undergo response assessment or come off study before response assessment for disease progression will be evaluable for response. CR will be defined as complete metabolic response or negative biopsy in the setting of residual PET avidity. Although there are marked differences in progression free survival for patients with early stage disease (stage I,II) versus advanced stage disease (stage III, IV), complete response rate to treatment (such as SMILE) is similar regardless of stage. Therefore, for the primary objective, early stage and advanced stage patients will be analyzed together. Early stage disease is more common and thus we expect that 66% of patients enrolled onto this study will have early stage disease. If pembrolizumab is efficacious in untreated ENKTL, the treatment approach evaluated in this study will be evaluated in a larger phase II study. Based

upon expression of PD-L1 in ENKTL and experience in the relapsed/refractory setting, we expect that the clinical or pathologic complete response rate to pembrolizumab in untreated disease will be at least 40%. We plan to enroll 19 patients with untreated ENKTL. Assuming a complete response rate of 40%, the 95% confidence interval with a sample size of 19 is 0.18-0.62, i.e. the width of the interval is 0.44. Patients who are removed prior to the first response evaluation will be counted as non-responders.

This study is expected to enroll 19 patients over 2 years.

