# 4.2 Intervention

# Early Stage (Stage I, II) ENKTL

Newly diagnosed patients with early stage disease will initially receive 2 cycles of single-agent pembrolizumab, 200mg IVPB every 3 weeks followed by reassessment by PET. Patients with no evidence of disease progression will receive another 2 cycles of pembrolizumab. In addition, patients with an "indeterminant response" by the LYRIC criteria (evidence of disease progression on PET but with clinical improvement) can be considered for another 2 cycles of pembrolizumab after discussion with the MSK PI.1 Patients who progress to stage III or IV ENKTL will come off treatment and receive subsequent standard of care treatment at the discretion of the treating physician. After 4 cycles of pembrolizumab, patients achieving complete response will receive involved site radiation (ISRT) and an additional 6 months of maintenance pembrolizumab. Patients who do not achieve complete response to pembrolizumab will undergo a biopsy. Those with pathologic complete response to treatment will receive the same treatment as those achieving complete response on PET (involved site radiation and an additional 6 months of maintenance pembrolizumab). Patients with less than complete response by PET or biopsy after 4 cycles of pembrolizumab will proceed to 2 cycles of SMILE chemotherapy and involved site radiation.

(Refer to Stage I, II Schema in Section 1.0 Protocol Summary)

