# Advanced Stage (Stage III, IV) ENKTL

Newly diagnosed patients with advanced stage disease will initially receive 2 cycles of single-agent pembrolizumab, 200mg IVPB every 3 weeks followed by reassessment by PET. Patients with no evidence of disease progression will receive another 2 cycles of pembrolizumab. In addition, patients with an "indeterminant response" by the LYRIC criteria (evidence of disease progression on PET but with clinical improvement) can be considered for another 2 cycles of pembrolizumab after discussion with the MSK PI. After 4 cycles of pembrolizumab, those who achieve a partial metabolic response (PMR) to pembrolizumab will proceed to 3 cycles of SMILE chemotherapy, involved site radiation therapy (if indicated and according to institutional standards), followed by 10 months maintenance therapy with pembrolizumab. Patients who do not achieve partial metabolic response to pembrolizumab will undergo biopsy. Those with biopsy showing persistent lymphoma will come off study and receive treatment per discretion of treating physician. If the biopsy shows pathologic complete response to therapy, patients will receive the same treatment as those with PMR.

(Refer to Stage III, IV Schema in Section 1.0 Protocol Summary)

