# 9.0 TREATMENT/INTERVENTION PLAN

#### 9.1 Stage I, II ENKTL

Newly diagnosed patients with early stage disease will initially receive the following study treatment:

- Baseline FDG-PET/CT simulation will be done following an initial consultation in Radiation Oncology (main center) and prior to starting therapy
- 2 cycles of single-agent pembrolizumab, 200mg IVPB every 3 weeks
- Reassessment by PET after 2 cycles of pembrolizumab
  - o If no evidence of disease progression, another 2 cycles of pembrolizumab.
  - Patients with an "indeterminant response" by the LYRIC criteria (evidence of disease progression on PET but with clinical improvement) can be considered for another 2 cycles of pembrolizumab after discussion with the MSK PI.
  - Patients with progression of disease without evidence of clinical improvement will proceed to 2 cycles of SMILE chemotherapy and ISRT.
  - Patients who progress to stage III or IV ENKTL will come off treatment and receive subsequent standard of care treatment at the discretion of the treating physician.
- Reassessment by PET after 4 cycles of pembrolizumab
  - If CR response on PET, patients will begin 45 Gy of involved site radiation (ISRT) and an additional 6 months of maintenance pembrolizumab. ISRT will begin 2-6 weeks after cycle 4 of pembrolizumab.
  - Patients with less than CR will undergo a biopsy. If biopsy shows no evidence of lymphoma, patients will proceed with same treatment as those with PET CR.

 Patients with less than complete response by PET and persistent evidence of disease on biopsy after 4 cycles of pembrolizumab will proceed to 2 cycles of SMILE chemotherapy and ISRT.

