# 9.2 Stage III, IV ENKTL

Newly diagnosed patients with advanced stage disease will obtain baseline FDG-PET/CT simulation after a Radiation Oncology consultation. They will initially receive 2 cycles of single-agent pembrolizumab, 200mg IVPB every 3 weeks followed by reassessment by PET. Patients with no evidence of disease progression will receive another 2 cycles of pembrolizumab. In addition, patients with an "indeterminant response" by the LYRIC criteria (evidence of disease progression on PET but with clinical improvement) can be considered for another 2 cycles of pembrolizumab after discussion with the MSK PI. After 4 cycles of pembrolizumab, those who achieve a partial metabolic response (PMR) to pembrolizumab will proceed to 3 cycles of SMILE chemotherapy, up to 50.4 Gy of involved site radiation therapy (if determined to be appropriate by a Radiation Oncology Attending and according to institutional standards), followed by 10 months maintenance therapy with pembrolizumab. Patients who do not achieve partial metabolic response to pembrolizumab will undergo biopsy. Those with biopsy showing evidence of lymphoma will come off study and receive treatment per discretion of treating physician. If the biopsy shows no evidence of lymphoma, patients will receive the same treatment as those with PMR.

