- 15. **Pembrolizumab**: Pembrolizumab is administered every 3 weeks (21 days) on Day 1 of each cycle, ± 3 days. Pembrolizumab is given 200m via IVPB infusion over 30 minutes (+/- 5 minutes).
- 16. **Reassessment by PET after 4 Cycles of pembrolizumab**: If Partial Metabolic Response (PMR) by PET, patients may begin 45 Gy of involved site radiation (ISRT) if indicated, and an additional 6 months (8 cycles) of maintenance pembrolizumab. ISRT will begin 2-6 weeks after Cycle 4 of pembrolizumab. Patients with less than PMR will undergo a biopsy. If biopsy shows no evidence of lymphoma, patients will proceed with same treatment as those with PET CR. Patients with less than PMR by PET and persistent evidence of disease on biopsy after 4 cycles of pembro will be taken off study.
- 17. **Follow-up** includes: standard clinic visit and laboratory tests (CBC, comp only). EBV PCR every 3 months for 3 years. Imaging to be obtained every 6 months for 2 years post treatment. cfDNA to be collected 6 months, 1 year, and 2 years into follow up or until a new therapy is initiated.
- 18. PET/CT to be completed at baseline only if the patient will not be receiving radiation therapy.
- 19. Patients will be followed by PET/CT (skull apex to midthigh) If PET/CT is not feasible, patients may be followed with CT CAP plus CT nasal cavity (for patients with nasal cavity disease) after discussion with MSK PI. If followed by PET/CT, additional diagnostic CT is NOT required.
- 20. PET/CT to be done after last cycle of SMILE only may be done prior to treatment on C5D1. All other assessments marked should be done for every cycle of SMILE.
- 21. cfDNA to be collected at C1D1, C4D1, C5D1 of pembrolizumab, end of treatment, and 6 months, 1 year, and 2 years into follow up or until a new therapy is initiated.

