# 12.0 CRITERIA FOR STAGING AND THERAPEUTIC RESPONSE/OUTCOME ASSESSMENT

Patients with ENKTL will be staged using the Ann Arbor criteria prior to initiation of treatment (outlined in Table 8. Response to treatment will be assessed using the Lugano Classification. Definitions for response are outlined in Table 9 below. In addition to the criteria described below, patients with residual PET-avidity, but with a biopsy showing no evidence of lymphoma, will be considered CR. Furthermore, although the Lugano Classification defines partial metabolic response (PMR) simply as "reduced FDG-uptake compared to baseline", normal variations in FDG-avidity of lesions can be observed between PET scans. To avoid declaring normal variations in SUV as PMR, we will use the definition

of PMR defined by PERCIST which defines PMR as 30% or more reduction in SUV from baseline. 12

Responses for patients with evidence of disease progression on PET will be further classified using the LYRIC criteria (outlined in Table 10 below) when appropriate.

Table 8 Ann Arbor Staging Criteria

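### The pooled primary CR rate counts a negative biopsy, but the post-cycle-4 biopsy trigger differs by stage, and sections conflict on whether a stage III–IV partial metabolic responder is biopsied

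*Combined protocol and SAP*

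**What the plan says.** Section 14.0, Primary objectives, sets the endpoint: "CR will be defined as complete metabolic response or negative biopsy in the setting of residual PET avidity". It adds that "for the primary objective, early stage and advanced stage patients will be analyzed together". Section 12.0 gives the same biopsy rule for response assessment: "patients with residual PET-avidity, but with a biopsy showing no evidence of lymphoma, will be considered CR". Neither section limits the rule by stage or by the purpose of the biopsy, and neither gives a time window.

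The treatment plan sets the biopsy after cycle 4 by stage.

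- **Stage I–II.** Section 4.2: "Patients who do not achieve complete response to pembrolizumab will undergo a biopsy". Section 9.1: "Patients with less than CR will undergo a biopsy". Footnote 17 of the Section 10.1 calendar agrees.
- **Stage III–IV.** Section 4.2 (and 9.2 likewise): "those who achieve a partial metabolic response (PMR) to pembrolizumab will proceed to 3 cycles of SMILE chemotherapy". Section 9.2: "Patients who do not achieve partial metabolic response to pembrolizumab will undergo biopsy". Footnote 16 of the Section 10.2 calendar has the same trigger: "Patients with less than PMR will undergo a biopsy".

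Two other places go further and do not separate the stages. Section 10.3 (Tissue biopsies) provides for a biopsy after four cycles in every patient without a complete metabolic response. Footnote 13, under both calendars, makes a cycle 4 research biopsy (days 8–20) compulsory for all participants, unless the site of disease makes it an unnecessary risk.

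**The concern.** When a negative biopsy can turn a PET-positive patient into a CR, the rule for who is biopsied is part of how the endpoint is measured. Under Sections 4.2, 9.1 and 9.2, a stage I–II PMR is biopsied and can become a CR. A stage III–IV PMR is given no biopsy, although a stage III–IV patient with a worse PET result is. Two consequences follow.

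- The pooled rate combines two strata measured by different rules. Section 14.0 justifies pooling by saying that CR rates to treatment such as SMILE are similar across stages. Unequal ascertainment could create or hide a stage difference, so the trial's own data could not check that premise.
- Within stage III–IV the ordering is reversed: a below-PMR patient with a negative biopsy is classed as CR, above a patient with PMR.

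Because Section 10.3 and footnote 13 point the other way, two sites could each comply with the protocol and classify the same stage III–IV PMR patient differently on the primary endpoint. Section 7.0 names an external institution as well as the lead centre.

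**Working it through.** **1. Routes to a biopsy-based CR after cycle 4**

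| PET after cycle 4 | Stage I–II, Section 9.1 | Stage III–IV, Section 9.2 | Either stage, Section 10.3 |
|---|---|---|---|
| Complete metabolic response | CR by PET | CR by PET | CR by PET |
| PMR | biopsy; CR if negative | no biopsy stated; not CR | biopsy; CR if negative |
| Below PMR | biopsy; CR if negative | biopsy; CR if negative | biopsy; CR if negative |

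The strata differ only in the PMR row, and only if Section 10.3 and footnote 13 are not applied or their biopsies are not counted.

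**2. The plan's own precision figure.** Inputs from Section 14.0 are p = 0.40 and n = 19. The half-width is 1.96 × √(0.40 × 0.60 / 19) = 0.220, which gives 0.18 to 0.62 and a width of 0.44. This reproduces the stated interval, which is not in dispute.

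**3. Size of the affected stratum.** Section 14.0 expects 66% early stage. Stage I–II: 0.66 × 19 = 12.5 patients. Stage III–IV: 0.34 × 19 = 6.5, so 6 or 7 patients.

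**4. Effect of one patient.** One stage III–IV PMR who would have been biopsy-negative, but is not biopsied, lowers the pooled rate by 1/19 = 0.053. Relative to the planned half-width this is 0.053 / 0.220 = 0.24. For scale, 8/19 = 42.1% has an exact 95% interval of 20.3–66.5%, and 7/19 = 36.8% has 16.3–61.6%.

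**5. Range under assumptions.** The documents give neither a PMR rate (r) nor the share of PMRs with a negative biopsy (q). If Section 9.2 is followed alone, the expected fall in the pooled rate is 0.34 × r × q, and the artificial gap between stages is r × q.

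- Assumed r = 0.20, q = 0.10: 0.34 × 0.02 = 0.7 points, or 19 × 0.0068 = 0.13 patients; gap 2 points.
- Assumed r = 0.40, q = 0.50: 0.34 × 0.20 = 6.8 points, or 19 × 0.068 = 1.3 patients; gap 20 points.

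If Section 10.3 is followed and its biopsies count, the fall is zero.

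**The case against.** The strongest reply is that the sections can be read together. Section 9.2 says which result leads to which treatment; it does not forbid a biopsy in a PMR. It is not a complete assessment plan either, since it does not mention complete metabolic responders. Section 10.3 and footnote 13 supply the biopsy, and Sections 12.0 and 14.0 count a negative result in either stage. On that reading there is no asymmetry. This is a fair reading, and it is why the effect may be zero. It does not settle the matter: the correlatives section and a research-biopsy footnote would have to override the treatment plan's own trigger, and Section 14.0 does not say that such biopsies count or when they must be taken.

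It is also fair to say that the effect is small and lowers the CR rate, in an estimation-only pilot. A PET-only rate does not repair the composite either; it only gives a figure measured by one rule.

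Some stronger readings are tempting but are not supported.

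- A reader might infer that a stage III–IV PMR can never be a CR. Section 10.3 and footnote 13 contradict that.
- A reader might infer from the calendars that the cycle 4 biopsy comes before or after the PET. Both sit in one day 14–21 column, which fixes no order.
- A reader might cite footnote 16 of the stage III–IV calendar as confirming that a PMR goes to SMILE. It supports the below-PMR biopsy trigger but does not mention SMILE.
- The schema footnote that makes biopsy optional concerns results below PMR, so it says nothing on whether a PMR is biopsied.

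**Conclusion.** The concern holds as a conflict between sections that bears on the primary endpoint. The treatment plan gives unequal biopsy access to CR in two strata that are pooled, and other passages would remove the inequality if followed and counted. The documents do not show that the CR rate will be biased, and they do not allow the size to be estimated. What can be said is 5.3 points per affected patient, with 6–7 of 19 patients in the stratum at risk. Under the assumed ranges above, the expected number is between 0.13 and 1.3 patients if Section 9.2 is followed alone, and none under Section 10.3. The direction is conservative, and no formal decision threshold could be crossed. The change should be made because the result depends on which passage a site follows and because the remedy is cheap.

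**What to change.** 1. Reconcile the stage III–IV text in Sections 4.2 and 9.2 and footnote 16 with footnote 13 and Section 10.3. This review takes no view on which biopsy rule is right. Then state in Section 14.0 which biopsies count toward CR and their window relative to the cycle 4 PET, in the same terms for both stages.
2. Beside the primary rate, report a supportive PET-only complete metabolic response rate after cycle 4, using the Table 9 definition, the same evaluable population and an exact 95% confidence interval. This applies one rule in both stages.
3. If the reconciled text leaves a stage III–IV PMR unbiopsied, say in Section 14.0 that the composite is not ascertained equally by stage and is to be read with the PET-only rate.

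Rates by stage are optional and descriptive only, given 6–7 patients in the smaller stratum.

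The cost is reconciliation of existing text, a few sentences in Section 14.0, and one or two table rows from scans already scheduled. The drawback is that the PET-only rate can only equal or fall below the composite, so the report will carry a second figure that may look less favourable.

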### **Secondary objectives:**

The secondary objectives of the study are safety of the treatment program, overall response rate (ORR) and partial metabolic response (PMR) rate to pembrolizumab, progression free survival (PFS), and overall survival (OS). Adverse events related to treatment will be tabulated and analyzed using descriptive statistics. ORR and PMR rates will be assessed after 4 cycles of pembrolizumab and calculated along with an exact 95% confidence interval. Progression free survival (PFS) and overall survival (OS) will be calculated using the method of Kaplan-Meier. Time origin for PFS and OS are time of treatment initiation. PFS and OS will be analyzed separately for early and advanced stage patients.

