# **Secondary objectives:**

- Assess safety of pembrolizumab as front line therapy for ENKTL.
- Assess the partial response rate and overall response rate of pembrolizumab in untreated ENKTL.
- Assess response after 2 cycles of pembrolizumab according to the LYRIC criteria
- Determine 2-year progression free survival and overall survival for newly diagnosed ENKTL treated with pembrolizumab-based therapy
- Explore mechanism of action and markers of response and resistance through assessment of baseline and on-treatment biopsies
- Evaluate plasma Epstein-Barr virus (EBV) PCR as a marker of response to therapy and/or early predictor of relapse.

\*Patients with PET showing less than partial metabolic response may undergo biopsy to evaluate for persistent disease after discussion with PI.

\*\*Or biopsy showing no evidence of lymphoma

\*\*\*Patients with an "indeterminant response" by the LYRIC criteria (evidence of disease progression on PET but with clinical improvement) can be considered for another 2 cycles of pembrolizumab after discussion with the MSK PI. See section 9.2 for details.

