# 11.2 Causality

Using the following criteria, the relationship of the AE to the study drug should be assessed as follows:

- Yes: The event is suspected to be related if:
  - There is a clinically plausible time sequence between onset of the AE and administration of study treatment; and/or
  - There is a biologically plausible mechanism for the study treatment to cause or contribute to the AE; and/or

- The event responds to withdrawal of the study intervention (dechallenge) and/or recurs with rechallenge (when clinically feasible); and/or
- The AE cannot be reasonably attributed to concurrent/underlying illness, other drugs, or procedures

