#### No:

- The AE is more likely to be explained by the subject's clinical state, underlying disease, concomitant medication, study or non-study procedure; and/or
- The time of occurrence of the AE is not reasonably related to administration of study treatment; and/or
- The event is unlikely to be related to the investigational procedures(s)

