# 11.3 Adverse Events Reporting Procedures

All AEs (e.g., any new event or worsening in severity or frequency of a pre-existing condition or laboratory finding) with an onset date after the subject signs consent for study participation must be promptly documented on the appropriate summary. Details of the event must include severity, relationship to study drug, duration, action taken, and outcome.

All AEs that are considered related to study procedures must be followed to resolution or stabilization if improvement is not expected.

AEs should be reported from the time the subject signs consent through 30 days post-last study intervention. In addition, the Investigator should report any AE that may occur after this time period that is believed to have a reasonable possibility of being associated with study intervention. If a subject discontinues study prior to receiving any study intervention, AEs must be reported through the end-of-study visit. AEs which completely resolve and then recur should be recorded as a new AE. For subjects who complete the end of study visit less than 30 days following the last study intervention, a follow up of ongoing AEs should be attempted by telephone and documented in the subject's source. AEs continuing at 30 days post-last treatment should have a comment in the source by the Investigator that the event has stabilized or is not expected to improve.

The Principal Investigator is responsible for evaluating all AEs, obtaining supporting documents, and determining that documentation of the event is adequate. Adverse events will be assigned a severity grade using the NCI CTCAE grading scale v4.0 and recorded. Furthermore, the occurrence of grade 2 or higher immune-related adverse events will be collected and designated as immune-related events of clinical interest (irAEs).

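### Section 14.0 tabulates only treatment-related adverse events, through an ambiguous relatedness rule, so the safety objective has no planned all-cause table

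*Combined protocol and SAP*

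**What the plan says.** Section 14.0 (Secondary objectives) describes the aim broadly: "The secondary objectives of the study are safety of the treatment program". The analysis that follows is narrower: "Adverse events related to treatment will be tabulated and analyzed using descriptive statistics". No other section plans an adverse-event table, a breakdown by grade or a summary of irAEs. Section 2.0 words the same objective differently: "Assess safety of pembrolizumab as front line therapy for ENKTL".

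Relatedness is defined in Section 11.2, which opens: "Using the following criteria, the relationship of the AE to the study drug should be assessed as follows". The Yes list has four items, the first being "There is a clinically plausible time sequence between onset of the AE and administration of study treatment; and/or". The No list has three, the first being "The AE is more likely to be explained by the subject's clinical state, underlying disease, concomitant medication, study or non-study procedure; and/or". The items in both lists are joined so that any one is enough.

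Collection under Section 11.3 is not restricted. Its rule begins "All AEs (e.g., any new event or worsening in severity or frequency of a pre-existing condition or laboratory finding" and runs from consent to 30 days after the last study intervention. Severity and relationship to study drug are recorded for each event, and grade 2 or higher immune-related events are designated separately.

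**The concern.** Safety is the first-listed secondary objective, and Section 14.0 says a larger phase II study will follow if pembrolizumab is efficacious. Section 3.0 gives SMILE's toxicity as the reason for seeking a less toxic approach in early-stage disease. A reader of the results will therefore want the total toxicity burden, and will want to know in which part of treatment it arose.

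The planned table shows neither. Events pass first through an unblinded Yes/No judgement with no comparator arm behind it. That judgement is hard in this population. Section 4.2 admits patients with HLH regardless of the haematological entry criteria and describes cytopenias as characteristic of HLH, so a low count on treatment can plausibly be put down to either the disease or the drug. Two investigators who both follow Section 11.2 could rate the same event differently, and only one of the two ratings puts it in the table.

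**Working it through.** **The plan's own figure.** The documents state no safety figure. The only design calculation is the interval for an assumed 40% complete response rate with n = 19. It reproduces as a Wald interval: 0.40 ± 1.96 × √(0.40 × 0.60 / 19) = 0.40 ± 0.220, or 0.18 to 0.62. It does not bear on safety, and nothing below changes it.

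**Step 1: can one event meet both lists?** Take an event that starts a few days after an infusion but is more likely due to the lymphoma. Its timing meets the first Yes item, and one Yes item suffices. Its likelier explanation meets the first No item, and one No item suffices. Section 11.2 does not say which rating prevails.

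**Step 2: related to what?** Section 11.2 opens with the study drug, and Section 11.3 records relationship to study drug. Section 5.1.1 identifies the study drug as pembrolizumab. The individual Yes items, however, speak of study treatment and study intervention. Section 14.0 speaks of the treatment program, and Sections 4.2 and 9 put SMILE and ISRT in that program. Section 17.2 asks for relationship to the treatment or treatments, but only for serious events. Whether a non-serious SMILE or ISRT toxicity enters the table depends on which wording the rater follows.

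**Step 3: direction against all-cause events.** Patients with a related event are a subset of patients with any event, so the related-only rate is equal or lower.

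*Illustration; the counts are assumed.* Suppose 10 of 19 patients have a grade 3 or higher event of any cause: 10/19 = 52.6% (exact 95% interval 28.9% to 75.6%).

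| Patients with at least one such event rated related | Related-only rate | Gap to all-cause |
|---|---|---|
| 10 | 52.6% | 0 points |
| 8 | 42.1% | 10.5 points |
| 5 | 26.3% | 26.3 points |
| 2 | 10.5% | 42.1 points |

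Each patient moves the rate by 1/19 = 5.3 points.

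**Step 4: direction against treatment-caused events.** Let 6 patients have a treatment-caused event and 6 others only events that treatment did not cause (assumed). The true rate is 6/19 = 31.6%. If the rating has sensitivity *s* and specificity *c*, the expected tabulated rate is [6*s* + 6(1 − *c*)]/19.

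| *s* | *c* | Tabulated rate | Against the true 31.6% |
|---|---|---|---|
| 0.7 | 1.0 | 4.2/19 = 22.1% | too low |
| 0.7 | 0.7 | (4.2 + 1.8)/19 = 31.6% | no net bias |
| 0.9 | 0.5 | (5.4 + 3.0)/19 = 44.2% | too high |

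The sign depends on how the ambiguous rule is applied, and the documents do not settle that.

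**The case against.** The strongest reply is that the gap is one reporting sentence in a 19-patient descriptive pilot. Every event is recorded with grade and relationship. Immune-related events are flagged. Section 17.2 requires serious-event reporting without a relatedness condition during the reporting window, and Section 17.2.1 (which applies to the lead centre only) says the same explicitly for reports to the drug supplier. Section 16.2 provides DSMC review. No test, stopping rule or sample size depends on the table, and an all-cause table could be produced at any time. All of this stands. It limits the weight of the point and makes the remedy cheap, but it does not make the all-cause table part of the plan.

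Two stronger readings are tempting, and the documents support neither.

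- A reader might infer that the table will understate toxicity caused by treatment. Timing alone is enough for a Yes, which with three-weekly dosing can over-attribute, while the No list can under-attribute. Excluding an event that treatment did not cause is not an error, so multiplying an all-cause rate by an assumed share called related does not measure bias.
- A reader might infer that SMILE and ISRT events are certainly left out. The tabulation sentence follows directly on the treatment-program objective, so its reference to treatment can fairly be read to cover them. What the documents show is an inconsistency in terms.

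**Conclusion.** The point holds in this form. The planned safety analysis is limited to related events although all events are collected. The relatedness rule has overlapping criteria with no tie-break, and its reference (study drug) does not match the stated objective (treatment program). With a single arm, the result can only equal or fall below all-cause toxicity, and it may err in either direction for treatment-caused toxicity.

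The size is unknown. The documents give no adverse-event rate and no expected share rated related, so the gaps of 0 to 42 points and the rates of 22.1% to 44.2% in the working are illustrations on assumed inputs. The one firm figure is 5.3 percentage points per patient. The primary endpoint and the sample size are unaffected. The change is worth making because the plan, followed as written, gives a less informative safety result than the data allow.

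**What to change.** 1. In Section 14.0, replace the tabulation sentence with: *All adverse events, regardless of attribution, will be tabulated by worst CTCAE grade per patient and by treatment phase, with treatment-related events and grade 2 or higher irAEs shown as subsets.* The phases would be pembrolizumab cycles 1 to 4, SMILE, ISRT and maintenance.
2. Reconcile the study-drug wording in Sections 11.2 and 11.3 with the treatment program in Section 14.0, so that it is clear whether relatedness covers pembrolizumab alone or each component.
3. State in Section 11.2 which rating applies when an event meets both the Yes and the No criteria. Without this, the related subset stays ambiguous even after item 1.

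**Cost.** Item 1 costs one more descriptive table and uses data that Section 11.3 already requires. Items 2 and 3 are short text edits; if relatedness is to be rated for each component, the adverse-event form may need a further field. The safety figures may look less favourable than a related-only table would.
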